5.3. Exploratory Objectives

The exploratory objectives of the study are as follows:

- To assess the effect of treatment with solanezumab as demonstrated using the MMSE.
- To assess the utility of a novel computerized battery, the Computerized Cognitive Composite (C3), in predicting and tracking clinical decline and response to solanezumab.
- To assess the effects of treatment on healthcare resource utilization.
- To determine the best predictors of clinical decline based on the PACC.
- To develop novel sensitive outcome measures to improve the efficiency of future secondary prevention trials, including exploratory measures of self-reported assessment of cognitive and interpersonal functioning.
- To assess the effect of treatment with solanezumab as demonstrated using the Clinical Dementia Rating (CDR) scale.
- To assess the effect of treatment with solanezumab as demonstrated using the C-Path Consortium’s Participant-Reported Outcome Questionnaire (C-Path PRO).
- To investigate the impact of solanezumab on markers of synaptic dysfunction on functional connectivity MRI.
- To test the hypothesis that solanezumab reduces brain tau burden, as compared with placebo, as assessed using flortaucipir positron emission tomography (PET) imaging.

- To assess solanezumab-associated changes in levels of plasma A β species and CSF A β species. The hypothesis that solanezumab, unlike placebo, alters amyloid-plaque associated forms of A β will be assessed by 1) demonstrating presence of plaque-associated A β species in the plasma, and 2) confirming that concentrations of CSF free (unbound to antibody) A β_{1-42} are increased or unchanged and CSF free A β_{1-40} levels are decreased with solanezumab treatment.
- To explore whether baseline markers of neurodegeneration (volumetric MRI or CSF tau or p-tau) are related to cognitive decline and response to treatment with solanezumab.
- To explore the impact of disclosure of amyloid status on questionnaires probing perception of amyloid imaging and concern about developing AD.
- To explore biomarker assessments collected at baseline and at the end of the placebo-controlled period as potential predictors of treatment effect during the open-label period.
- To assess preclinical AD during open-label treatment by comparing participants initially randomized to solanezumab in the placebo-controlled period with participants initially randomized to placebo in the placebo-controlled treatment period, using randomized/delayed-start analysis of the RUI-B.

[figure not shown]
6. Study Design

6.1. Summary of Study Design

Study A4 is a multicenter, randomized, double-blind, placebo-controlled, Phase 3 study comparing solanezumab with placebo for 240 weeks in approximately 1150 participants ages 65 to 85 years old with preclinical AD, defined as having evidence of brain amyloid pathology without clinically evident cognitive impairment at screening. Participants who met entry criteria were randomized in a 1:1 ratio (approximately 575 per treatment arm) to solanezumab or placebo once every 4 weeks. Participants were randomized within the site by education – high (13 or more years) or low (12 or less years) and the presence of one or more apolipoprotein E gene (APOE) ϵ 4 alleles (yes, no). The primary hypothesis being tested is that the cognitive decline at the end of the placebo-controlled period will be significantly less for solanezumab than for placebo. Participants completing the placebo-controlled period of the study can opt to participate in the open-label period of the study that will last for up to 204 weeks or until the primary analyses of the placebo-controlled period of the study are completed and reviewed.

At the beginning of the COVID-19 pandemic, a hiatus was implemented to allow participants to pause study activities without missing visits and resume when COVID safety mitigations were in place (for example, vaccines, home infusions, etc.). The hiatus extended the end of the placebo-controlled period for up to 9 months and the placebo-controlled period will be administratively closed in December 2022.

Figure A4.SAP.1 illustrates the study design.

Abbreviation: V = visit.

Figure A4.SAP.1. Illustration of study design for Clinical Protocol A4.

6.2. Determination of Sample Size

In order to develop an appropriate measure of cognitive decline in a preclinical population, we tested several combinations of measures using data from longitudinal studies in clinically normal populations, including the ADNI; the AIBL; the ADCS-PI trial; and the HABS.

Sample size and power at 4.5 years (240 weeks) for the PACC were estimated using data from ADNI and HABS. Estimates were obtained by applying appropriate assumptions regarding treatment difference, SD, and attrition for a 4.5-year study in a preclinical AD population. In ADNI, the difference in the composite change between participants with and without elevated brain amyloid at 240 weeks was 2.13 (SD=2.85). Similarly, in HABS, the difference in the composite change between participants with and without elevated brain amyloid at 240 weeks was 2.66 (SD=3.08). Given the ADNI-derived estimate of SD at 240 weeks of SD=2.85 and 30% attrition, the total N=1150 provides 80% power (5% 2-sided alpha) to detect a treatment difference of 0.532 points or $0.532/2.13 = 24.9\%$ of the amyloid group difference. Similarly, based on the HABS estimate of SD at 240 weeks of SD=3.08, the study has 80% power to detect a treatment difference of 0.570 points or $0.570/2.66 = 21.4\%$ of the amyloid group difference.

For the open-label period, the estimated mean PACC difference between cognitively normal participants with and without elevated brain amyloid at 336 weeks is 2.95 (SD=3.77) based on ADNI and 4.74 (SD=3.99) based on HABS. Accounting for the administrative censoring that will be induced by the common close design of the open-label period, and assuming an overall attrition rate of 30%, about 266 PACCs are expected to be available at 336 weeks. The visit-to-visit correlation is estimated to be about 0.5. Under these pilot estimates, 266 PACCs at 336 weeks would provide 80% power to detect a randomized group (early-start vs delayed-start treatment with solanezumab) difference of about 0.9 PACC points. This change of 0.9 PACC points reflects 30% of the difference between amyloid-positive and -negative participants based on ADNI, and 20% of that difference based on HABS.

Sample size for the study was determined assuming an MMRM analysis prior to the interruption caused by the COVID-19 pandemic. Applying the NCS approach in simulated trials with a COVID-19 pandemic interruption suggests the study has 94% power to detect an effect size of 0.75 PACC points at 240 weeks.

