7.1.5. Open-Label Extension Period

Subjects who complete the placebo-controlled period will be eligible to participate in the open-label extension period. Subjects participating in the open-label period will receive open-label solanezumab treatment for varying durations. While all subjects will receive solanezumab treatment during the open-label period, subjects, site personnel, and study teams will remain blinded to initial treatment assignment in the placebo-controlled period until the conclusion of the study.

The open-label period uses a common close design such that all subjects will complete the period at the same time: when analyses of the placebo-controlled period are completed and reviewed. Given the common close design, the overall duration of treatment for each patient will differ. If the study is positive, participants may be offered the opportunity to continue in the open-label period beyond the common close. Subjects who opt to participate in the open-label period should begin the open-label period at Visit 66 (Week 240) after completion of all Visit 66 tests and procedures. However, subjects may enter the open-label period of the study and receive their first open-label infusion of study drug up to 12 weeks following completion of the placebo-controlled period Visit 66 assessments and procedures. In extenuating circumstances, subjects may enter the open-label period after 12 weeks with the approval of a Medical Monitor and/or Project Director. See the Study Schedule ([Attachment 1](#)) for the timing of events and measures to be assessed. Procedures for some visits may take more than 1 day.

Subjects who choose not to participate in the open-label period will not receive any study medication after the last infusion visit for the placebo-controlled period (Week 236). Sites must obtain approval from the Coordinating Center before engaging in open-label activities.

If the open-label period is extended beyond Visit 117, participants who complete Visit 117 before implementation of the protocol amendment that includes additional visits will be allowed to resume study visits once available at their site.

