11.1. Determination of Sample Size

In order to develop an appropriate measure of cognitive decline in a preclinical population, we tested several combinations of measures using data from longitudinal studies in clinically normal populations, including the ADNI; the AIBL; the ADCS-PI trial; and the HABS ([Attachment 3](#)).

Sample size and power at 4.5 years (240 weeks) for the PACC were estimated using data from ADNI and HABS. Estimates were obtained by applying appropriate assumptions regarding treatment difference, SD, and attrition for a 4.5-year study in a preclinical AD population. In ADNI, the difference in the composite change between subjects with and without elevated brain amyloid at 240 weeks was 2.13 (SD=2.85). Similarly, in HABS, the difference in the composite change between subjects with and without elevated brain amyloid at 240 weeks was 2.66 (SD=3.08). Given the ADNI-derived estimate of SD at 240 weeks of SD=2.85 and 30% attrition, the total N=1150 provides 80% power (5% 2-sided alpha) to detect a treatment difference of 0.532 points or $0.532/2.13 = 24.9\%$ of the amyloid group difference. Similarly, based on the HABS estimate of SD at 240 weeks of SD=3.08, the study has 80% power to detect a treatment difference of 0.570 points or $0.570/2.66 = 21.4\%$ of the amyloid group difference.

For the open-label period, the estimated mean PACC difference between cognitively normal subjects with and without elevated brain amyloid at 336 weeks is 2.95 (SD=3.77) based on ADNI and 4.74 (SD=3.99) based on HABS. Accounting for the administrative censoring that will be induced by the common close design of the open-label period, and assuming an overall attrition rate of 30%, about 266 PACCs are expected to be available at 336 weeks. The visit-to-visit correlation is estimated to be about 0.5. Under these pilot estimates, 266 PACCs at 336 weeks would provide 80% power to detect a randomized group (early-start vs delayed-start treatment with solanezumab) difference of about 0.9 PACC points. This change of 0.9 PACC points reflects 30% of the difference between amyloid-positive and -negative participants based on ADNI, and 20% of that difference based on HABS.

Sample size for the study was determined prior to the interruption caused by the COVID-19 pandemic. Applying the NCS approach in simulated trials with a COVID-19 pandemic interruption suggests the study has 94% power to detect an effect size of 0.75 PACC points at 240 weeks.

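### The same 30% attrition is used at Week 240 and at Week 336, so the expected 266 PACCs allow for no open-label dropout or refusal, unless the Week 240 figure is too pessimistic

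*SAP*

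**What the plan says.** SAP 6.2 and Protocol 11.1 carry the same sizing text.

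- **Week 240.** Protocol 11.1: "Given the ADNI-derived estimate of SD at 240 weeks of SD=2.85 and 30% attrition, the total N=1150 provides 80% power", for a difference of 0.532. With the HABS SD of 3.08, "the study has 80% power to detect a treatment difference of 0.570 points".
- **Week 336.** The expected count is built in one sentence: "Accounting for the administrative censoring that will be induced by the common close design of the open-label period", and then "assuming an overall attrition rate of 30%, about 266 PACCs are expected to be available at 336 weeks". The amyloid group difference "at 336 weeks is 2.95 (SD=3.77) based on ADNI and 4.74 (SD=3.99) based on HABS". With a visit-to-visit correlation of about 0.5, 266 PACCs are said to give 80% power for a difference of about 0.9 points between early and delayed start.
- **The extension is optional.** SAP 6.1: "Participants completing the placebo-controlled period of the study can opt to participate in the open-label period of the study". Protocol 7.1.5 provides for refusals: "Subjects who choose not to participate in the open-label period will not receive any study medication after the last infusion visit". The open-label schedule in Protocol Attachment 1 has an early-termination column.

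Neither document gives an attrition rate for Weeks 240 to 336, an extension take-up rate, or the share of participants expected to reach Week 336 before the common close.

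**The concern.** Attrition accumulates. If 30% have left by Week 240, overall attrition at Week 336 can be 30% only if nobody leaves in the next 96 weeks and every completer enters the extension. The second condition sits badly with a design in which entry is a choice. The plan makes no separate allowance for either loss, since the only other reduction it names is the common close.

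What is at stake is the number of Week 336 PACCs the sponsor should expect, and so whether the stated 80% power for the early- versus delayed-start difference is likely to be reached. Week 336 is the time point of the main open-label efficacy analysis (Protocol 11.2.10, SAP 7.9.3.2).

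**Working it through.** **Step 1: what the 30% at Week 240 means.** Inputs from SAP 6.2: N = 1150 (575 per arm), two-sided 5%, 80% power, SD 2.85 or 3.08.

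- Completers only: 1150 x 0.70 = 805, or 402.5 per arm. Detectable difference = (1.960 + 0.842) x SD x sqrt(2/402.5) = 0.563 and 0.608. These exceed the printed 0.532 and 0.570.
- MMRM information formula: ten post-baseline PACC visits (every 24 weeks), exchangeable correlation 0.5, dropout rising linearly to 30% at Week 240. This gives 0.530 and 0.573, close to the printed figures.

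The 30% therefore behaves as cumulative attrition at Week 240.

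**Step 2: what lies behind 266.** The count cannot be derived, because no censoring fraction is printed. Working backwards, 266/(0.70 x 1150) = 266/805 = 33% of those retained would reach Week 336 before the close. Equivalently, 266/0.70 = 380 exactly, which fits 380 participants reaching Week 336 times 0.70 with no further factor. This is an inference, not something the plan says.

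**Step 3: the two 30% figures together.** Under a constant hazard (my assumption; the plan states none):

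- 30% at Week 240 gives retention of 0.70^(336/240) = 0.607 at Week 336, or 39% attrition.
- 30% at Week 336 gives retention of 0.70^(240/336) = 0.775 at Week 240, or about 22% attrition (22.5%).

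**Step 4: illustration.** Hold the 33% factor fixed and accept the printed 80% at 266 for 0.9 points, two-sided 5% (the general rule in SAP 7.1; the power paragraph gives no alpha for Week 336).

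- n = 266 x (retention at Week 336 / 0.70) x take-up
- Power by count = Phi(2.802 x sqrt(n/266) - 1.960)
- Difference at 80% power by count = 0.9 x sqrt(266/n)

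Example: 266 x 0.607/0.70 = 231, and Phi(2.802 x sqrt(231/266) - 1.960) = 74%. The MMRM column scales the standard error by the Step 1 model, extended to the four open-label PACC visits through Week 336.

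| Dropout after Week 240 | Take-up (assumed) | PACCs at Week 336 | Power by count | Power, MMRM | Difference at 80% power, by count |
|---|---|---|---|---|---|
| None | 100% | 266 | 80% (printed) | 80% | 0.90 |
| None | 90% | 239 | 76% | 76.5% | 0.95 |
| None | 80% | 213 | 71% | 72% | 1.01 |
| Constant hazard | 100% | 231 | 74% | 75% | 0.97 |
| Constant hazard | 90% | 208 | 70% | 71% | 1.02 |
| Constant hazard | 80% | 185 | 65% | 67% | 1.08 |

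**Step 5: how firm the anchor is.** With 133 per arm and SD 3.77, power at 0.9 is 49.5% unadjusted, 61% with the variance multiplied by 0.75 (1 - 0.5 squared), and 78.6% with the variance halved. With SD 3.99 the figures are 45%, 57% and 74%. The exchangeable-0.5 MMRM gives a detectable difference of 1.05 to 1.11 at 266. The printed 80% is approached only with the ADNI SD and the variance halved, so the table shows relative losses from an anchor that depends on an unstated use of the correlation.

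**The case against.** A reader might infer that 266 is simply too high. The documents do not support that, because the censoring fraction is not given. Under the same constant hazard, 266 would still be right if 266/(1150 x 0.607) = 38% of those retained reached Week 336 before the close at full take-up, or 48% at 80% take-up, instead of 33%. The inconsistency also runs the other way: 30% may be right for Week 336 and too pessimistic for Week 240. Both points stand.

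A reader might also infer that the 80% power statement is false. It is conditional on having 266 PACCs, so attrition does not falsify it; only the expectation of reaching 266 is in doubt. Nor do the documents say that completers are expected to decline. They only provide for those who do. The constant hazard and the 80-90% take-up are assumptions of this review.

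The consequence is limited in three further ways, all of which stand. The 0.9-point figure concerns the early- versus delayed-start difference (the second hypothesis in SAP 7.9.3.2), not the noninferiority test with the 50% margin, for which no loss is computed here. Delayed-start analyses proceed only if the Week 240 contrast is significant (Protocol 11.2.10). The Week 336 model uses all randomized participants (SAP 7.9.3.2), which softens the loss.

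None of this reconciles the two printed attrition figures, and the missing fraction is a further reason to restate the calculation, since nobody can check 266 without it.

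**Conclusion.** The point holds in limited form. Two printed inputs are compatible only with no dropout after Week 240 and full take-up of an optional extension. Either the 266 PACCs make no allowance for open-label dropout or refusal, or the Week 240 attrition is set too high.

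On the first reading, the illustrative loss is moderate. Power at 0.9 points falls from 80% to 74-75% at full take-up, 70-71% at 90% and 65-67% at 80%, and the difference detectable with 80% power rises from 0.90 to about 0.97-1.08 by count. These figures rest on a constant dropout hazard, assumed take-up, the back-calculated 33% factor held fixed, and the printed 80% at 266. They should not be copied into the plan as replacements.

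The Week 240 primary power is not weakened; on the alternative reading its attrition input is conservative.

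**What to change.** In SAP 6.2 and Protocol 11.1:

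1. State the cumulative attrition assumed at Week 240 and, separately, at Week 336, so that the second carries the first forward.
2. State the assumed extension take-up.
3. State the share expected to reach Week 336 before the common close.
4. Recompute the expected Week 336 count and the power for the early- versus delayed-start difference, saying how the 0.5 correlation enters and which alpha is used.

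Observed counts are preferable to assumptions. The SAP approval is dated 18 January 2023, after the December 2022 close of the placebo-controlled period planned in SAP 6.1, so Week 240 completion and extension-entry counts pooled across arms should be obtainable without unblinding. They would also reflect the COVID-19 hiatus of up to 9 months, which changes the calendar behind the censoring; correcting attrition alone would not make 266 accurate.

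The cost is a short recalculation and revised wording in two sections. The stated count and power may become less favourable. No hypothesis, margin, primary power or study conduct changes.

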6.3. Method of Assignment to Treatment

Participants who met all criteria for enrollment were randomized in a 1:1 ratio to double-blind treatment at baseline (Visit 6). For between-group comparability, participants were randomized within site by education – high (13 or more years) or low (12 or less years), and by the presence of one or more APOE ε4 alleles (yes, no). Assignment to treatment groups was determined by a computer-generated random sequence.

7. A Priori Statistical Methods

7.1. General Considerations

Unless otherwise noted, all tests of treatment effects will be conducted at a 2-sided alpha level of 0.05; 2-sided confidence intervals will be displayed with a 95% confidence level. All tests of interactions between treatment and other factors will be conducted at an alpha level of 0.05.

All analyses will follow the modified intent-to-treat (mITT) principle unless otherwise specified. An ITT analysis is an analysis of data by groups to which the participants are assigned by random allocation, even if the participant does not take the assigned treatment, does not receive the correct treatment, or otherwise does not follow the protocol. An mITT analysis is an ITT analysis for all participants who have a baseline and at least 1 postbaseline measure. All safety analyses will be done using the safety population. Analysis populations are described below (Section 7.5).

When change from baseline is assessed, participants will be included in the analysis only if both a baseline and a post-baseline measure are available. Unless otherwise defined, a baseline measure is the last non-missing observation collected prior to the first infusion of study medication. End point is the last non-missing post-baseline measurement.

For MMRM analyses, observations collected at non-scheduled visits (see Section 7.2) will not be included in the analyses. For NCS and MMRM analyses, unless otherwise specified, an unstructured covariance structure will be used. If the unstructured covariance structure matrix results in a lack of convergence, the following covariance structures will be used in sequence: heterogeneous Toeplitz covariance structure, heterogeneous autoregressive covariance structure, heterogeneous compound symmetry covariance structure and homogeneous compound symmetry covariance structure.

7.2. Handling of Dropouts or Missing Data

If any of the individual items for any of the clinical scales are missing or unknown, every effort will be made to obtain the score for the missing item or items. For the primary outcome (PACC), if one of the four components is missing, the total score will be imputed. The sum of the other three components will be prorated to the sum of total components. The imputed number will be rounded up to the nearest integer. If the nearest integer is greater than the maximum possible score, the imputed score will be equal to the maximum score. If more than one of the components is missing, the PACC at that visit will be considered missing.

For the ADL Prevention Questionnaire, if $\leq 30\%$ of the items are missing, the total score will be imputed. The sum of the non-missing items will be prorated to the sum of total items. The imputed number will be rounded up to the nearest integer. If the nearest integer is greater than the maximum possible score, the imputed score will be equal to the maximum score. If $>30\%$ of the items are missing, the total score at that visit will be considered missing.

The same imputation technique will be applied to the CFI, CDR-SB and MMSE.

For the FCSRT, the total score will be imputed if only 1 of the three trials of cued scores is missing – if any of the free recall scores are missing or if more than 1 cued recall scores are missing, the total will not be imputed and will be considered missing. The imputation will rely on the sensitivity to cueing measure, which is defined as the number of correct cued responses divided by the total number of cued responses across the two completed trials. For instance, if a participant was cued on 10 items and correctly answered on 8 of them, the sensitivity to cueing measure would be 0.8. This value will then be multiplied by the number of items the participant should have been cued on for the missing trial and the resulting value will be rounded to the nearest integer.

For all other scales, if any item is missing, any total or sum involving that item will be considered missing.

Analyses that treat time as a continuous variable (e.g. NCS and slope) will utilize every post-baseline observation in the placebo-controlled phase. Repeated measures analyses that treat time as a categorical variable (MMRM) will only use data from visits at which the data were scheduled to be collected (Andersen and Millen 2013). Amendment (e) of the protocol defined the acceptable window for efficacy scales to be 8 weeks. Therefore, if a scale is missing from a protocol-defined visit where the scale was to be assessed but present at a subsequent visit that is not more than 8 weeks after the protocol-defined visit and prior to the next protocol-defined visit at which the scale is to be assessed, then the late-assessed scale result will be “carried back” and used at the protocol-defined visit.

When participants discontinue from the study early, there may be efficacy or safety data measurements at visits at which the variables were not scheduled to be collected. These data will be used in all other analyses.

